10.9 Relationship of SAE to study drug or other intervention

An assessment of the relationship between the AE and the medical intervention. CTCAE does not define an AE as necessarily “*caused by a therapeutic intervention*”. After naming and grading the event, the clinical investigator must assign an attribution to the AE using the following attribution categories:

Relationship	Attribution	Description
Unrelated to investigational agent/intervention	Unrelated	The AE is clearly NOT related to the intervention
	Unlikely	The AE is doubtfully related to the intervention
Related to investigational agent/intervention	Possible	The AE may be related to the intervention
	Probable	The AE is likely related to the intervention
	Definite	The AE is clearly related to the intervention

For all collected AEs, the clinician who examines and evaluates the subject will determine the adverse event’s causality based on temporal relationship and his/her clinical judgment. The degree of certainty about causality will be graded using the categories below:

Definitely Related: There is clear evidence to suggest a causal relationship, and other possible contributing factors can be ruled out. The clinical event, including an abnormal laboratory test result, occurs in a plausible time relationship to drug administration and cannot be explained by concurrent disease or other drugs or chemicals. The response to withdrawal of the drug (de-challenge) should be clinically plausible. The event must be pharmacologically or phenomenologically definitive, with use of a satisfactory rechallenge procedure if necessary.

Probably Related: There is evidence to suggest a causal relationship, and the influence of other factors is unlikely. The clinical event, including an abnormal laboratory test result, occurs within a reasonable time sequence to administration of the drug, is unlikely to be attributed to concurrent disease or other drugs or chemicals, and follows a clinically reasonable response on withdrawal (de-challenge). Rechallenge information is not required to fulfill this definition.

Possibly Related: There is some evidence to suggest a causal relationship (e.g., the event occurred within a reasonable time after administration of the trial medication). However, the influence of other factors may have contributed to the event (e.g., the subject’s clinical

condition, other concomitant events). Although an adverse drug event may rate only as “possibly related” soon after discovery, it can be flagged as requiring more information and later be upgraded to “probably related” or “definitely related”, as appropriate.

Unlikely: A clinical event, including an abnormal laboratory test result, whose temporal relationship to drug administration makes a causal relationship improbable (e.g., the event did not occur within a reasonable time after administration of the trial medication) and in which other drugs or chemicals or underlying disease provides plausible explanations (e.g., the subject’s clinical condition, other concomitant treatments).

Unrelated: The AE is completely independent of study drug administration, and/or evidence exists that the event is definitely related to another etiology. There must be an alternative, definitive etiology documented by the clinician.

10.10 Treatment Dose Modifications and Guidelines for Adverse Event Reporting specific to study drug

Dose modifying hematological and non-hematological toxicities are defined differently. Dose modification or discontinuation of trametinib for toxicity is considered a dose modifying toxicity. Guidelines for management and dose modifications are also provided for the toxicities of special interest.

Trametinib Dose Modification Schedule for Adverse Events

Grade (CTC-AE)*	Schedule
	Grade (CTC-AE)* Dose Modifications
Grade 1 or Grade 2 (Tolerable)	Continue treatment and monitor as clinically indicated.
Grade 2 (Intolerable) or Grade 3	Interrupt therapy until toxicity is grade 0-1 and reduce by one dose level when resuming therapy.
Grade 4	Discontinue permanently, or interrupt therapy until Grade 0 to 1 and Reduce by one dose level when resuming therapy.

* The intensity of clinical adverse events graded by the Common Terminology Criteria for Adverse Events v4.0 (CTC-AE)

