10.2.1.1 Non-Hematological Dose-Modifying Toxicity

- See [Section 10.2.6](#) for management guidelines for toxicities of special interest. Note that dose modification or discontinuation of trametinib for toxicity is considered a dose modifying toxicity.
- Any Grade 4 non-hematological toxicity with specific exclusion of:
 - Grade 4 fever/pyrexia that resolves to Grade < 2 within 72 hours with supportive care (anti-pyretics)
- Dose-modifying hypertension will be considered as the following:
 - Grade 4 hypertension,
 - A blood pressure > 25 mm Hg above the 95th percentile for age, height, and gender, confirmed by repeated measurement

Note: if elevated, take 3 serial blood pressure readings from the same extremity with the patient in the same position, separated by at least 5 minutes. Avoid using the lower extremity if possible. Use the mean average of the 3 measurements.

- Any Grade 3 non-hematological toxicity with the specific exception of:
 - Grade 3 nausea and vomiting of less < 3 days duration

- Grade 3 fever or infection < 7 days duration.
- Grade 3 hypophosphatemia, hypokalemia, hypocalcemia and/or hypomagnesemia responsive to oral supplementation within 7 days
- Grade 2 allergic reactions that necessitate discontinuation of study drug will not be considered a dose-modifying toxicity
- Any Grade 2 non-hematological toxicity that persists for ≥ 7 days and is considered sufficiently medically significant or sufficiently intolerable by patients that it requires treatment interruption
- Grade 2 left ventricular ejection fraction disease
- Grade 2 cardiac valvular toxicity (mitral/aortic/tricuspid)
- Grade 2 pneumonitis
- Treatment interruption longer than 14 days due to delayed recovery from toxicity will be cause for dose modification

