10.2.3 Dose Modifications for Non-Hematologic Toxicity

If a subject experiences a dose-modifying non-hematologic toxicity as defined in [Section 10.2.1](#), the treatment will be held.

If the toxicity does not resolve to meet inclusion/exclusion parameters or baseline within 14 days of drug discontinuation the subject must be removed from protocol therapy unless specifically documented in toxicities of special interest [Section 10.2.6](#).

If the toxicity resolves to meet inclusion/exclusion parameters or baseline within 14 days of drug discontinuation the subject may resume treatment with a reduction to the next lower dose according to [Appendix II](#). See [Appendix II](#) for dosing modification in subjects receiving oral solution or the specified dose reduction in subjects receiving tablets.

- Doses reduced for toxicity will not be re-escalated, even if there is minimal or no toxicity with the reduced dose, unless otherwise specified in the toxicities of special interest [Section 10.2.6](#).
- If the same dose-modifying toxicity recurs in a subject who has resumed treatment, the subject must be removed from protocol therapy.

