10.2.4 Dose Modifications for Hematologic Toxicity

The study chair must be notified for any dosage modification or use of myeloid growth factors.

- If a subject experiences a dose modifying hematologic toxicity as defined in [Section 10.2.2](#), the treatment will be held until improvement to Grade 3 or less.
- Subjects will be allowed 1 episode of Grade 4 hematologic toxicity without dose reduction.
- If there is > 1 hold for Grade 4 hematologic toxicity, dose will be reduced per guidance in [Appendix II](#). Counts should be checked twice weekly during this time.
- Doses reduced for toxicity will not be re-escalated, even if there is minimal or no toxicity with the reduced dose.
- If dose-modifying toxicity recurs in a subject who has resumed treatment at the reduced dose, the subject must be removed from protocol therapy.

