10.2.5 Dose Modifications for Hepatic Toxicity

If a subject experiences Grade ≥ 3 ALT or AST or total bilirubin elevation, treatment will be held. If toxicity resolves to meet eligibility criteria within 7 days, the drug may be resumed at the same dose. Grade ≥ 3 ALT or AST or bilirubin that persists ≥ 7 days will be considered dose-modifying and require dose modification per [Section 10.1.3](#).

Grade	0	1	2	3	4
SGOT (Serum glutamic oxaloacetic transaminase) (AST)	WNL	>ULN to 3x ULN	>3 to 5x ULN	>5 to 20x ULN	>20x ULN
SGPT (Serum glutamic pyruvic transaminase) (ALT)	WNL	>ULN to 3x ULN	>3 to 5x ULN	>5 to 20x ULN	>20x ULN
Bilirubin	WNL	>ULN to 1.5x ULN	>1.5 to 3x ULN	>3 to 10x ULN	>10x ULN

Safety Follow-Up Procedures for subjects with ALT or AST ≥ 3 times ULN or bilirubin ≥ 1.5 times ULN:

- Monitor subjects weekly until liver chemistries resolve, stabilize, or return to within baseline values.

Safety Follow-Up Procedures for subjects meeting DLT criterion as above (ALT or AST ≥ 5 times ULN and bilirubin ≥ 3 times ULN) greater than 7 days:

- This event is considered an DLT.
- Serum bilirubin fractionation should be performed if testing is available. If fractionation is unavailable, urinary bilirubin is to be measured via dipstick (a measurement of direct bilirubin, which would suggest liver injury).
- Subjects should have close follow-up for repeat liver chemistries, additional testing, and close monitoring (with specialist or hepatology consultation recommended).
- Monitor subjects twice weekly until liver chemistries (ALT, AST, ALP, and bilirubin) resolve, stabilize or return to within baseline values.

- In addition, every attempt should be made to carry out the liver event follow-up assessments described below:
 - Viral hepatitis serology, including:
 - Hepatitis A IgM antibody
 - Hepatitis B surface antigen and Hepatitis B Core Antibody (IgM)
 - Hepatitis C RNA
 - Cytomegalovirus IgM antibody
 - Epstein-Barr viral capsid antigen IgM antibody (or if unavailable, then obtain heterophile antibody or monospot testing)
 - Serum creatine kinase (CK) and lactate dehydrogenase (LDH).
 - Fractionate bilirubin, if total bilirubin ≥ 2 X upper limit of normal (ULN).
 - Obtain a complete blood count (CBC) with differential to assess eosinophilia.

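### The general dose-modification table in Section 10.10 contradicts the event-specific rules in Section 10.2, and the protocol does not say which prevails

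*Protocol*

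**What the plan says.** Section 10.10 contains a stand-alone trametinib dose-modification schedule by CTCAE grade. Tolerable Grade 1 or 2: continue. Intolerable Grade 2 or Grade 3: "Interrupt therapy until toxicity is grade 0-1 and reduce by one dose level when resuming therapy". Grade 4: stop permanently, or interrupt to Grade 0-1 and reduce one level. No exceptions are listed. The text above the table notes that separate guidelines exist for toxicities of special interest, without ranking them against the table. The footnote names CTCAE v4.0.

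Section 10.2 sets its own rules:

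- **10.2.1.1** counts Grade 3 non-hematologic toxicity as dose-modifying with exceptions, among them "Grade 3 fever or infection < 7 days duration", nausea and vomiting under 3 days, and electrolyte changes that respond to oral supplements within 7 days. An intolerable Grade 2 event counts, in general, only if it lasts at least 7 days; Grade 2 LVEF, valvular and pneumonitis events are listed without that limit. It adds: "Note that dose modification or discontinuation of trametinib for toxicity is considered a dose modifying toxicity".
- **10.2.3** sets the recovery standard for non-hematologic events: "If the toxicity resolves to meet inclusion/exclusion parameters or baseline within 14 days of drug discontinuation the subject may resume treatment" one level lower. Recurrence has a consequence: "If the same dose-modifying toxicity recurs in a subject who has resumed treatment, the subject must be removed from protocol therapy".
- **10.2.4** (hematologic): "the treatment will be held until improvement to Grade 3 or less", and "Subjects will be allowed 1 episode of Grade 4 hematologic toxicity without dose reduction".
- **10.2.5** (ALT, AST or bilirubin of Grade 3 or higher): "If toxicity resolves to meet eligibility criteria within 7 days, the drug may be resumed at the same dose".
- **10.2.6.4, 10.2.6.7 and 10.2.6.8** maintain the dose for asymptomatic Grade 3 CPK, allow no reduction after Grade 3 diarrhea that resolves within 72 hours, and restart Grade 2-3 visual events at the same dose once RPED and RVO are excluded.

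**The concern.** The two sets of instructions address the same events and differ both on whether the dose is reduced and on how far toxicity must resolve before restart. A site following 10.10 reduces for an event that 10.2 exempts. A site following 10.2 need not reduce, although it may still interrupt under 10.1.2.

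The difference persists. Under 10.2.3 and 10.2.4 a dose reduced for toxicity is not re-escalated, apart from exceptions in 10.2.6, and Appendix II has only one lower level. Because a dose modification for toxicity is itself classed as a dose-modifying toxicity (10.2.1.1, repeated in 10.10), a reduction made under 10.10 can turn an exempt event into a counted one. If that event recurs, 10.2.3 can then require removal from therapy. Exposure before the primary assessment, and the count of dose-modifying toxicities, can thus vary with the section read across a consortium of 25 sites.

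**Working it through.** The protocol states no figure to reproduce on this point. The check sets the rules side by side and then sizes one dose step.

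**1. Same event, two instructions**

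| Event | 10.10 table | 10.2 |
|---|---|---|
| Grade 3 fever or infection under 7 days | Interrupt to Grade 0-1, reduce | Not dose-modifying (10.2.1.1) |
| Grade 3 nausea/vomiting under 3 days; electrolytes corrected orally within 7 days | Interrupt, reduce | Not dose-modifying (10.2.1.1) |
| Grade 3 ALT/AST/bilirubin meeting eligibility limits within 7 days | Interrupt, reduce | Hold, then same dose allowed (10.2.5) |
| First Grade 4 hematologic episode | Stop, or Grade 0-1 and reduce | No reduction (10.2.4) |
| Hematologic recovery level | Grade 0-1 | Grade 3 or less (10.2.4) |
| Grade 3 CPK, asymptomatic | Interrupt, reduce | Maintain dose (10.2.6.4) |
| Grade 3 diarrhea resolved within 72 h | Reduce | No reduction allowed for (10.2.6.7) |
| Grade 3 visual event, RPED and RVO excluded | Reduce | Same dose (10.2.6.8) |
| Grade 2 valvular toxicity, tolerated | Continue | Dose-modifying, so hold (10.2.1.1, 10.2.3) |

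The last row shows the conflict also running in the less protective direction. Grade 3 rash and Grade 2-3 pneumonitis essentially agree in both places: recovery to about Grade 1, then reduction.

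**2. Recovery level.** The AST eligibility limit in 5.1 is 5 x ULN. In the 10.2.5 grading table, Grade 2 AST runs from above 3 to 5 x ULN. Section 10.2 therefore permits restart at Grade 2 AST, while 10.10 requires Grade 0-1. For hematologic toxicity, 10.2.4 permits restart at Grade 3, a grade at which 10.10 requires a stop.

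**3. Precedence.** The only ranking stated is in 10.2.3, which gives way to 10.2.6 and does not mention 10.10. The pointer in 10.10 concerns toxicities of special interest. The list in 10.2.6 is rash, CK/CPK, ejection fraction, pneumonitis, diarrhea, visual disturbance, hypertension and paronychia. Fever, infection, vomiting, electrolyte, hepatic, hematologic and valvular events are not on it.

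**4. CTCAE version.** The 10.10 footnote says v4.0. Sections 2.1, 3.3, 10.2.6.11 and 10.6 say v5.0. The contradictions above do not depend on the version.

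**5. Size of one reduction.** From Appendix II, reduction = 1 - (level -1 dose / level 1 dose):

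| Weight (kg) | Level 1 to level -1 (mg) | Reduction |
|---|---|---|
| 10.0-10.9 | 0.2 to 0.2 | 0% |
| 11-11.9 | 0.25 to 0.22 | 12% |
| 12-22.9 (five bands) | 0.3 to 0.24; 0.35 to 0.28; 0.4 to 0.32; 0.45 to 0.36; 0.5 to 0.4 | 20% each |
| 23-24.9 | 0.6 to 0.46 | 23% |
| 25-29.9 | 0.7 to 0.5 | 29% |
| 30-34.9 | 0.8 to 0.6 | 25% |
| 35-50 | 1 to 0.75 | 25% |
| 50.1-70 | 1.5 to 1 | 33% |
| 70.1 and over | 2 to 1.5 | 25% |

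At 35-50 kg the reduced dose exists only as oral solution, so a subject on tablets would also change formulation. The 9.0-9.9 kg row is left out: its level 1 entry is the 0.0125 mg/kg starting dose (0.12 mg), and its level -1 entry is 0.18 mg.

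**The case against.** The strongest reply is that most of the Section 10.2 rules permit and do not require. A hepatic event may resume at the same dose; one Grade 4 hematologic episode is allowed without reduction; the 10.2.1.1 exceptions define what counts and forbid nothing. A site taking the stricter 10.10 line would breach few of them, the clearest case being the instruction to maintain the dose for asymptomatic Grade 3 CPK. That is true of a site that reduces. It does not help a site that uses the permission, because 10.10 requires what that site has left undone.

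A second reply is that specific guidance ordinarily outranks a general table. That is a reasonable reading for CPK, diarrhea and visual events, to which 10.10 points. It does not reach the events off the special-interest list, and the protocol never states the principle.

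Third, the 10.10 heading suggests drug toxicity only, and its footnote speaks of clinical events, so coverage of isolated laboratory grades is arguable. Even on that reading, drug-attributed fever, infection, vomiting and diarrhea still conflict.

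Some of the case against stands. A qualifying Grade 3 non-hematologic toxicity is held and restarted one level lower under both sections. Appendix IX sets count thresholds for starting a cycle (ANC above 1,000, platelets above 75,000), which limits restarts at low counts in practice. The route to removal needs a 10.10 reduction, reclassification and recurrence, and in 10.2.1.1 the reclassifying sentence sits in the bullet on special-interest toxicities, although 10.10 repeats it in general terms. Dose before cycle 6 also varies by design, through the half-dose start, approved escalation to 0.032 mg/kg and interruptions of up to 60 days.

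**Conclusion.** The concern holds. As written, Section 10.10 requires interruption and reduction for events that Section 10.2 exempts or lets resume at the same dose. It also sets a stricter recovery level than 10.2.4 and, for AST, than 10.2.5. Nothing in the protocol resolves this.

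Per affected subject the difference is one Appendix II step against no required reduction: 25% to 33% from 35 kg upward, and 0% to 29% on solution from 10 to 34.9 kg. It generally lasts for the remaining treatment. This assumes that the site applies the table literally and that the subject is at dose level 1. How many subjects would be affected cannot be derived. The effect is on exposure, on the classification of dose-modifying toxicity and on what monitoring would call a deviation. The response thresholds, sample size and Section 9.2 stopping rule do not change. It should be corrected, but it does not undermine the primary analysis.

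**What to change.** Preferred: delete the 10.10 table and refer the reader to Sections 10.2.1 to 10.2.6. Alternatively, keep the table and add a sentence stating that Sections 10.2.1 to 10.2.6 govern and that the table applies only to trametinib-attributable toxicity not addressed there. In either case, change any retained CTCAE reference in 10.10 from v4.0 to v5.0.

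The cost is protocol wording in one amendment. No assessments or subjects are added.

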10.11 IRB/IEC Notification of SAEs and Other Unanticipated Problems

The Investigator will promptly notify the IRB of record of all on-site unanticipated, serious Adverse Events that are related to the research activity. Other unanticipated problems related to the research involving risk to subjects or others will also be reported promptly. Written

reports will be filed with the IRB of record and in accordance with the timeline below. External SAEs that are both unexpected and related to the study intervention will be reported promptly after the investigator receives the report.

Type of Unanticipated Problem	Initial Notification (Phone, Email, Fax)	Written Report
Internal (on-site) SAEs Death or Life Threatening	24 hours	Within 2 business days
Internal (on-site) SAEs All other SAEs	7 days	Within 7 business days
Unanticipated Problems Related to Research	7 days	Within 7 business days
All other AEs	N/A	Brief Summary of important AEs may be reported at time of continuing review

10.11.1 Follow-up report

If an SAE has not resolved at the time of the initial report and new information arises that changes the investigator's assessment of the event, a follow-up report including all relevant new or reassessed information (e.g., concomitant medication, medical history) should be submitted to the IRB. The investigator is responsible for ensuring that all SAE are followed until either resolved or stable.

10.12 Investigator Reporting of a Serious Adverse Event to Coordinating Center

Any serious adverse event that is life threatening or causes death (as defined in [Section 10.7](#) above) whether anticipated or not, must be reported to the coordinating center (CHOP) within one business day of the investigator becoming aware of the event (expedited reporting). Events that are not life-threatening and do not result in death, must be reported within 7 business days of discovery. If only limited information is initially available, follow-up reports are required until resolution. The original SAE Form must be kept on file at the study site.

Reporting will be conducted in full accordance with all applicable Institutional Research Policies and Procedures and all applicable Federal and state laws and regulations including 45 CFR 46, and the Good Clinical Practice: Consolidated Guideline approved by the International Conference on Harmonization (ICH).

10.13 Medical Emergencies

For any medical emergencies, the Investigator or her physician designee will be responsible for investigating the emergency and resolving issues surrounding the emergency. Study

teams and medical personnel associated with the subject will proceed accordingly to provide best care.

10.14 Reporting of Study Treatment Errors Including Misuse/Abuse

Medication errors are unintentional errors in the prescribing, dispensing, administration or monitoring of a medicine while under the control of a healthcare professional, participant or consumer (EMA definition).

Misuse refers to situations where the medicinal product is intentionally and inappropriately used not in accordance with the protocol.

Abuse corresponds to the persistent or sporadic, intentional excessive use of a medicinal product, which is accompanied by harmful physical or psychological effects.

Study treatment errors and uses outside of what is foreseen in the protocol will be recorded on the appropriate CRF irrespective of whether or not they are associated with an AE/SAE. Study treatment errors and uses outside of what is foreseen in the protocol, including misuse or abuse, will be collected and reported in the safety database irrespective of it being associated with an AE/SAE within 24 hours of Investigator's awareness.

For more information on AE and SAE definition and reporting requirements, please see the respective sections.

11 STUDY ADMINISTRATION

11.1 IRB Approval

The Children's Hospital of Philadelphia (CHOP) Institutional Review Board (IRB) will serve as the reviewing IRB for this multi-center study. All participating sites have agreed to adhere to the single IRB (sIRB) Policy (<https://grants.nih.gov/grants/guide/notice-files/NOT-OD-16-094.html>) and to rely on CHOP as the sIRB.

The CHOP IRB will serve as a Privacy Board to fulfill the requirements of the Health Insurance Portability and Accountability Act (HIPAA) Privacy Rule (45 CFR 164.512(i)) for use or disclosure of protected health information for research purposes. The CHOP IRB has extensive experience with providing IRB oversight for external institutions and complies with the registration requirements for both the Office for Human Research Protections (OHRP) and the U.S. Food and Drug Administration (FDA) (IRB00000316 and IRB00000317). Prior to initiating the study, all participating sites will sign an authorization/reliance agreement that will clarify the roles and responsibilities of the sIRB and participating sites.

When the CHOP IRB serves as the reviewing IRB for other sites, it will need information from each relying institution about local context, consent form requirements (i.e. injury compensation language), applicable state/local laws and any local conflict of interest determinations. The CHOP IRB will provide approval notices and approved informed consent documents customized with the site Principal Investigator name, contact information and any other site-specific wording (i.e. injury compensation, HIPAA) for each relying institution.

As the sIRB, the CHOP IRB will communicate with the overall Principal Investigator through eIRB, which CHOP investigators also use for all other IRB submissions at CHOP. Communication with relying sites and their Principal Investigators will occur through the same system. This avoids the need to have the overall Principal Investigator collect the information from all of the relying sites and submit them to the CHOP IRB. eIRB provides the ability for Principal Investigators from each relying institution, after a simple registration process, to log in and provide site-specific documents and information (i.e. annual reports, site-specific recruitment materials) to the CHOP IRB. The CHOP IRB, in turn, will post site-specific packages (i.e. approval letters, stamped consent forms) for the use of the relying site Principal Investigators.

